0.920. In an open-label study in depressed adolescents. PCr levels following Cr administration increased by 6.2%+ 9.6%. In a dose-finding study of Cr compared to placebo, the effect size for differences in PCr levels between the group receiving 4 grams of Cr daily compared to placebo was 0.7. We hypothesize that supplementation with Cr with or without 5-HTP will increase frontal cortical PCr levels. P-MRS neuroimaging will be performed at baseline, and repeated after 8 weeks of treatment with Cr + placebo, 5-HTP + placebo, or 5-HTP + Cr. To address our first hypothesis, a population-averaged generalized estimating equation (GEE) regression model is used for group comparison of the  $\Delta PCr$  (PCrWEEK 8 - PCrBASELINE) associated with Cr + placebo, 5-HTP + placebo, or 5-HTP + Cr. We will control for age, gender, and tissue partial volume effects (i.e., gray matter, white matter and cerebrospinal fluid) for in vivo phosphorus metabolite measurements made at two time points. The GEE for each subject, i has the form Yi(t)=Xi  $\beta$  +  $\epsilon_i$ , where Yi and Xi represent measured metabolite (PCr or  $\beta$ -NTP) levels and design matrix of covariates, respectively. The error term follows a multivariate normal distribution:  $\varepsilon_i \sim N(0, V_i)$ , where Vi is the variance of metabolite levels. We assume that measures taken closer to each other in time are more highly correlated than those taken further apart. Therefore, the first-order autoregressive structure, AR(1) is assumed such as  $cov[\varepsilon_i(t), \varepsilon_j(t')] = \rho^{|t-1|}$ tVi to model the dependence of the correlation on repeated measures from the same participant, where t is time variable and p is the correlation coefficient between the clinical symptom measures of two successive assessments. Assuming  $\rho = 0.30$ , expected MDES = 5% across the groups, and harmonic mean SD = 10%, respectively, a sample size of 60 participants (15 per group; 4 aroups) and 2 neuroimaging time points per participant has >80% power using the AR (1) GEE model at the 0.05 alpha level. In our open-label study, we experienced ~20% participant attrition. Imputation of missing data cannot be utilized for neuroimaging data. Therefore, anticipating a 20% attrition rate, we propose a target enrollment of 75 participants for the R61 phase.

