2. Analysis of P-MRS Data: To analyze study data, a raw Hamming filter will be applied before performing 2D fast Fourier transformation, and each free induction decay (FID) will be linebroadened with 10 Hz of apodization. After Fourier transformation and frequency shift correction. zero-/first-order phase correction and baseline correction with polynomial interpolation will be applied. Spatial filtering with a Hamming window function will be implemented to reduce signal contamination from neighboring voxels. The preprocessed P-MRSI data will be fitted using jMRUI software with the Advanced Method for Accurate, Robust and Efficient Spectral (AMARES) fitting algorithm. Metabolites of interest include PCr, β-NTP, tP, and their ratios. From registered anatomical images, tissue segmentation will be performed using FSL (FMRIB's Software Library) software so that cerebrospinal fluid (CSF)-corrected metabolite concentrations as well as gray matter percentage in each voxel can be used as covariates in the analysis. Generalized estimating equations regression modeling will be used to evaluate group differences in metabolite levels controlling for age, sex, education level, and tissue partial volume effects (i.e. gray matter, white matter, CSF). Subjects with MDD will be compared to HCs at baseline and at follow-up. Sub-group analyses by gender will be included given evidence that Cr has been proposed as especially effective in women. Fisher's exact test will be used to compare groups on categorical variables.

**3. Analysis of Resting State Data:** As is seen in the small cohort of pilot data, we anticipate treatment groups to demonstrate increased global connectivity of the subgenual ACC after treatment, among other changes. A recent analysis determined that we can achieve single subject reproducibility of FC metrics of 0.16 Fisher-transformed correlation units. If we conservatively set the effect size at 8% and SD at 9% of mean, a sample size of 60 depressed subjects would achieve >90% power to detect significant treatment effects with the repeated measures design compared to baseline. For FC analyses, 361 regions of interest (ROIs) comprising a parcellation of cortical gray matter will be compared between placebo and active treatment subjects. We

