will conduct a second level of analysis using eight networks delineated as follows and derived from Gordon *et al.*: auditory, salience, frontoparietal, default, dorsal attention, ventral attention, sensorimotor, and visual. Two levels of analysis will be performed to balance multiple comparisons and granularity of spatial information. For each pair of 8 networks, mean BOLD time series will be extracted across the entire network and Fisher-transformed correlation coefficients will be calculated. An acceptable false discovery rate (q < .05) over all pairs of networks will be assumed to denote significant partial correlation with diagnosis. To evaluate which connections are anticorrelated, we will use an independent dataset for an unbiased estimate obtained from the S1200 Release of the Human Connectome Project (HCP) dataset. Group-wise ANOVA will be performed with false discovery rate correction for multiple comparisons across 361 x 361 connections tested for treatment group differences in FC before and after treatment compared to placebo group. Sub-group analyses by gender will be included given evidence that Cr has been proposed as especially effective in women. Subjects with MDD will be compared to HCs at baseline and at follow-up.

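### The >90% connectivity power fits an uncontrolled change from baseline in all 60 subjects, not the FDR-corrected placebo comparisons that the plan will run

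*Combined protocol and SAP*

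**What the plan says.** The only power statement for functional connectivity (FC) is in section e, item 3. The inputs are given in one clause: "conservatively set the effect size at 8% and SD at 9% of mean". The conclusion is that 60 depressed subjects "would achieve >90% power to detect significant treatment effects with the repeated measures design compared to baseline". No alpha is named and no allowance for multiple testing is mentioned. An alpha is printed only for the phosphocreatine calculation in item 1, which "has >80% power using the AR (1) GEE model at the 0.05 alpha level".

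The analysis that follows in item 3 is different in kind:

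- FC over 361 regions of interest is to be compared between subjects on placebo and subjects on active treatment.
- At connection level there is a group-wise ANOVA against the placebo group, with "false discovery rate correction for multiple comparisons across 361 x 361 connections tested for treatment group differences in FC before and after treatment". No q value is printed for this family.
- At network level, for 8 networks, the rule is: "An acceptable false discovery rate (q < .05) over all pairs of networks will be assumed to denote significant partial correlation with diagnosis". This is the only place in item 3 where q < .05 is printed, and it is worded for diagnosis, not treatment.

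Item 1 gives the allocation: 60 participants in four groups of 15.

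**The concern.** The power sentence speaks of treatment effects, but the design it names has no comparator. A change from baseline pooled over 60 people, 15 of them on double placebo, cannot separate treatment from time, regression to the mean or placebo response. The tests that could do so use a between-arm difference, with a larger standard error, and then a stricter threshold.

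Interpretation is what is at stake. If the connection-level map shows nothing, a reader who relies on a stated power above 90% could take that as evidence that the supplements do not change connectivity. The planned test may have had little chance of finding an effect of the assumed size.

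**Working it through.** **Inputs.** Effect 8% and SD 9% of the mean (e, item 3), so d = 8/9 = 0.889. Sixty subjects, 15 per arm (e, item 1). There are 8 × 7/2 = 28 network pairs and 361 × 360/2 = 64,980 unique connections.

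**Assumptions, because the plan is silent.** Two-sided 0.05; 9% is the SD of the change; tests are independent; the FDR procedure is Benjamini-Hochberg (BH) at q = .05 in both families and is applied to the treatment comparison.

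**Step 1: the plan's own figure.** Paired t-test, n = 60, noncentrality d√n = 0.889 × √60 = 6.89, 59 df.

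| Threshold | Power |
|---|---|
| 0.05 | >99.9% |
| 0.05/28 | 99.97% |
| 0.05/64,980 | 89% |

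So >90% reproduces as a lower bound, and for this test it largely survives correction.

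**Step 2: placebo-controlled contrasts, no correction.** Two-sample noncentrality is d√[n₁n₂/(n₁+n₂)] with n₁+n₂−2 df.

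| Contrast | Noncentrality | Power at 0.05 |
|---|---|---|
| 45 active v 15 placebo | 0.889 × √11.25 = 2.98 | 83% |
| 15 v 15 | 0.889 × √7.5 = 2.43 | 65% |
| 30 v 30 | 0.889 × √15 = 3.44 | 92% |

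For the four-group ANOVA (3 and 56 df), λ = 15 Σ(μᵢ − μ̄)²/9². With all three active arms shifted by 8, λ = 15 × 48/81 = 8.89 and power is 67%. With two arms shifted, λ = 15 × 64/81 = 11.85 and power is 81%.

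Only 30 v 30 passes 90%. Item 3 does not describe that split. A 1:1 grouping (5-HTP v no 5-HTP) appears only in item 4, for serotonin.

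**Step 3: BH over 28 network pairs** (average power per true effect, by simulation).

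| Truly affected pairs | 45 v 15 | 30 v 30 | 15 v 15 |
|---|---|---|---|
| 1 | 40% | 58% | 19% |
| 7 | 60% | 78% | 30% |
| 14 | 71% | 86% | 40% |
| 28 | 81% | 92% | 55% |

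**Step 4: BH over 64,980 connections.** With a share π truly affected, the working p-value threshold t solves t = q[(1−π)t + π × power(t)]. For 45 v 15 at π = 10%, t = 0.0022 and power(t) = 42%; check: 0.05 × (0.9 × 0.0022 + 0.1 × 0.42) = 0.0022.

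| Share affected | 45 v 15 | 30 v 30 | 15 v 15 |
|---|---|---|---|
| 0.1% | 1% | 7% | 0% |
| 1% | 10% | 29% | 0.1% |
| 5% | 30% | 54% | 4% |
| 10% | 42% | 65% | 10% |

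**Step 5: sensitivity to what the 9% means.** If it is the SD of a single scan, the SD of change is 9√[2(1−ρ)].

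- ρ = 0.3 (the value printed for phosphocreatine): SD 10.6%, d = 0.75. Unadjusted power is 70% for 45 v 15 and 82% for 30 v 30.
- ρ = 0.7: SD 7.0%, d = 1.15. For 45 v 15, power is 97% unadjusted and 71% at 0.05/28.
- ρ = 0.5 returns the SD of 9% used above.

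**The case against.** A reader might infer that the >90% can be obtained only at an unadjusted 0.05, so that the missing FDR allowance is the whole defect whichever contrast is used. The documents do not support that. The sentence names 60 subjects compared with baseline, and that paired test keeps 99.97% power at 0.05/28. Under BH at q = .05 it keeps at least 99% for true-effect shares from 0.1% upward. Only a full Bonferroni correction over 64,980 tests takes it just below, to 89%, and the plan does not use Bonferroni. The claim would be right for a 30 v 30 split, but reading that split into item 3 because its 92% resembles the printed figure works backwards from the answer.

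Three further points favour the sponsor:

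- The magnitudes depend on choices the documents do not settle: the meaning of 9%, the share of true effects, and independence among connections that share regions. This stands, and is why ranges are given. It does not restore the claim, because the plan states no inputs under which >90% would apply to the planned tests.
- Connectivity does not size the trial. Item 1 makes the phosphocreatine ratio the primary determinant, in a study described as proof of concept. This stands and limits the severity.
- The plan uses two levels of analysis partly to manage multiple comparisons. That is true, but no power is attached to either level.

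No passage says that a null map will be read as no effect; that is a risk, not a stated intention.

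**Conclusion.** The point holds as a mismatch between the contrast that was powered and the contrasts that will be tested. FDR correction widens the gap but is not its source. The printed >90% is correct for an uncontrolled pre-post change in 60 subjects. For 45 active v 15 placebo, the natural reading of item 3, power is 83% unadjusted, about 40 to 81% over 28 network pairs, and about 1 to 42% over connections with 0.1 to 10% affected. Pairwise 15 v 15 and the four-group ANOVA also miss 90% unadjusted. Among the corrected cases at d = 8/9, only 30 v 30 with nearly all network pairs affected reaches 90%.

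These figures assume two-sided 0.05, 9% as the SD of change, independent tests, and BH at q = .05 applied to treatment differences in both families. A scan-rescan correlation of 0.7, with 9% as a single-scan SD, would lift 45 v 15 to 97% unadjusted, but still only 71% at 0.05/28. The point deserves correction because the statement misdescribes the planned analysis, but it does not affect the trial's sample size.

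**What to change.** In section e, item 3:

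1. Name the placebo-controlled contrast (45 v 15, pairwise, factorial or four-group ANOVA).
2. State whether 9% is the SD of the change or of a single scan and, if the latter, the assumed correlation between scans.
3. Replace >90% with the power of that contrast under the FDR rule, separately for the 28 network pairs and the 361 × 361 family, over a stated range of truly affected shares. Alternatively, keep >90% and label it as applying only to uncontrolled change from baseline.
4. Print the alpha behind the calculation and the q for the connection-level family, and say whether the network rule, now worded for diagnosis, also governs the treatment comparison.
5. State that a null 361 × 361 map is not evidence of no effect.

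Naming the network family as the main connectivity test is an option for the sponsor; the point does not depend on it. The cost is some wording, one power calculation and a less favourable stated power. No extra patients or scans are needed.

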### **Introductory Statement and Study Protocol**

#### **Introductory Statement**

The proposed study is a single-center proof-of-concept study, targeting a volunteer sample of adults with MDD who have failed an adequate trial of an SSRI or SNRI. After screening (week -1) and baseline (week 0) assessments and baseline neuroimaging, 60 subjects (with recruitment of up to 75 subjects, allowing for 20% attrition) will be randomly assigned in 1:1:1:1 ratio to treatment for 8 weeks with either double placebo, 5-HTP 100mg twice daily + Cr-matched placebo, Cr 5g daily + 5-HTP-matched placebo, or 5-HTP 100mg twice daily + Cr 5g daily. The treatment phase will again be followed by neuroimaging (week 8) as well as two post-treatment assessments (weeks 10 and 12).

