After the screening visit, participants will have a **baseline** visit after one week with the MRI happening + 4 days from the baseline visit, prior to the start of treatment. At the baseline visit, the HAM-D17, MADRS, C-SSRS, BAI, YMRS, and CGI-S will be administered. Vital signs will be checked and a physical exam performed if patient symptoms indicate a need. Whole blood serotonin will be drawn. Subjects will be asked to be fasting for at least 3 hours prior to the blood draw. The blood draw will occur between 2 and 5pm to minimize circadian variation in serotonin levels. Participants will be evaluated for serotonin syndrome using the Hunter Criteria. Baseline P-MRS and resting state fcMRI will be completed. After initiation of treatment, **subjects will be** reevaluated at 1, 2, 4, 6, and 8 weeks (+3 days). At each these visits, the HAM-D17, MADRS, C-SSRS, BAI, YMRS, and CGI-S will be administered again. Subjects will be asked to be fasting for at least 3 hours prior to the blood draw. Whole blood serotonin will be drawn. The blood draw will occur between 2 and 5pm to minimize circadian variation in serotonin levels. Follow-up P-MRS and resting state fMRI will be completed at week 8. Vital signs with pulse oximetry, focused physical exam if indicated, collection of urine for pregnancy screening if indicated, recording of concomitant medications, self-reported drug use, medication compliance assessment, study medication dispensing, and screening for treatment-related adverse effects will also be undertaken. Screening for treatment-related adverse effects will include application of the Hunter Criteria for serotonin syndrome as well as evaluation for symptoms of eosinophilia-myalgia syndrome. If subjects exhibit symptoms of eosinophilia-myalgia syndrome, a CBC with automated differential will be obtained. Finally, participants will be seen for follow up visits at 2 weeks and 4 weeks (+3 days) after completion of 5-HTP/Cr supplementation. Measure at these visits will include the HAM-D17, MADRS, C-SSRS, BAI, YMRS, CGI, DESS, vitals with pulse oximetry if indicated, focused physical exam if indicated, and evaluation for serotonin syndrome and EMS. Again, if symptoms of EMS are present, a CBC with automated differential will be obtained. After the screening visit. Participants can request study visits by videoconference with the exception of briefly dropping by the clinic for a blood draw and/or MRI as indicated in the schedule below.

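### Connectivity power assumes a repeated-measures comparison with baseline, but the named group-wise ANOVA does not adjust for baseline connectivity or say how the two scans enter

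*Combined protocol and SAP*

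**What the plan says.** All of this is in the combined protocol and SAP, mainly section e. Statistical Design and Power, item 3 (Analysis of Resting State Data).

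- **Sizing.** The plan proposes to "conservatively set the effect size at 8% and SD at 9% of mean" and concludes that "a sample size of 60 depressed subjects would achieve >90% power to detect significant treatment effects with the repeated measures design compared to baseline".
- **Contrast.** The 361 regions of interest "will be compared between placebo and active treatment subjects".
- **Test.** "Group-wise ANOVA will be performed with false discovery rate correction for multiple comparisons across 361 x 361 connections", with those connections "tested for treatment group differences in FC before and after treatment compared to placebo group".
- **Design.** Participants are "randomly assigned in 1:1:1:1 ratio to treatment for 8 weeks", 15 per arm. FC is measured at baseline and again after treatment: "resting state fMRI will be completed at week 8" (Study Protocol, item c).

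The neighbouring biomarker analyses say more. Item 1 defines the PCr outcome as week 8 minus baseline and uses a GEE with AR(1) correlation, assuming 0.30. Item 4 analyses 5-HT with a linear mixed model for repeated measures. For FC, no change score, participant effect, baseline covariate or within-person correlation is stated.

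**The concern.** The power claim draws on each participant serving as their own reference. The named test does not say whether or how that happens. The wording fits at least three analyses: a separate ANOVA at each visit, an ANOVA on the week-8-minus-baseline change, or a repeated-measures ANOVA. They differ in power, sometimes widely, and which one does better depends on a correlation that the plan does not give. So the figure above 90% cannot be attached to the test that will be run.

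Two things are at stake. First, none of these readings adjusts week-8 FC for baseline FC, which is the efficient use of a baseline scan that every participant has anyway. Second, the choice stays open until the data are in, across a very large family of connections.

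**Working it through.** **Inputs**
- Effect 8% of mean and SD 9% of mean (item 3). The plan does not say whether 9% is the SD of one scan or of a change; one scan is assumed.
- 60 analysed participants, 15 per arm. Placebo against the three pooled active arms is 15 against 3 × 15 = 45.
- Two-sided alpha 0.05 for a single test: assumed, as item 3 gives none for its power statement.
- Within-person correlation ρ of FC: not given. Values 0.3, 0.5 and 0.7 are shown. The 0.30 in item 1 belongs to PCr.

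**1. The plan's own figure.** Standardised effect = 8/9 = 0.889. For a change from baseline in all 60, with 9% as the SD of that change, the noncentrality is 0.889 × √60 = 6.89 and power exceeds 99.9%. If 9% is the single-scan SD and ρ = 0, the SD of change is 9√2 = 12.73 and power is 99.8%. So the claim of more than 90% is met for a pre-post change in everyone. That is not a between-arm contrast.

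**2. SD of the analysed quantity**
- Week 8 only: 9
- Change score: 9√(2(1−ρ))
- Week 8 adjusted for baseline: 9√(1−ρ²)

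**3. Power, 45 v 15.** Noncentrality = 8 / (SD × √(1/45 + 1/15)) = 8 / (SD × 0.2981), with 58 df and critical value 2.002. Cells show SD; noncentrality; power.

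| ρ | Week 8 only | Change score | Baseline-adjusted |
|---|---|---|---|
| 0.3 | 9.00; 2.98; 83.4% | 10.65; 2.52; 69.8% | 8.59; 3.13; 86.7% |
| 0.5 | 9.00; 2.98; 83.4% | 9.00; 2.98; 83.4% | 7.79; 3.44; 92.3% |
| 0.7 | 9.00; 2.98; 83.4% | 6.97; 3.85; 96.6% | 6.43; 4.17; 98.4% |

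**4. Why the ordering does not depend on 8% and 9%.** The variance ratio of adjusted to change score is (1−ρ²)/(2(1−ρ)) = (1+ρ)/2, which is 0.65, 0.75 and 0.85 at the three values of ρ. Against week 8 only it is 1−ρ², which is 0.91, 0.75 and 0.51. Neither ratio exceeds 1 for ρ between 0 and 1.

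**5. One active arm v placebo, 15 v 15.** In the order week 8 only, change, adjusted: 65.2%, 51.1%, 69.3% at ρ = 0.3; 65.2%, 65.2%, 77.4% at 0.5; 65.2%, 85.8%, 90.8% at 0.7.

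**6. Cost of estimating the baseline slope.** The adjusted figures above ignore it. Inflating the variance by 1 + 1/(60−4) and using 57 df gives 86.1%, 91.8% and 98.2% for 45 v 15. With 1 + 1/(30−4) and 27 df, 15 v 15 gives 67.5%, 75.8% and 89.7%. The ordering is unchanged at these values of ρ. Only near ρ = 0 does week 8 alone do marginally better.

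**The case against.** The best defence is that the same short item calls the design repeated measures, so an ANOVA on change or a repeated-measures ANOVA is a natural reading. Either is valid, and so are separate ANOVAs at each visit, which use one scan per person. FC is also not the sizing endpoint: item 1 gives that role to PCr:tP, and the trial is a proof of concept. If FC is highly reproducible within a person, a change score is nearly as good as baseline adjustment (96.6% v 98.4% at ρ = 0.7).

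Most of this stands. A reader might go further and infer that each person's two scans are analysed as independent observations, so that the error rates, and with them the FDR step, are wrong. The documents do not support that. The error term would be wrong only in a group-by-time ANOVA with no participant term, and nowhere does the plan say that this will be run. Silence about the participant term is not a statement that it is absent.

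What the defence does not remove is that even the favourable readings leave baseline information unused or used less efficiently, and that the plan does not say which one applies.

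**Conclusion.** The point holds as a specification gap with an available gain in efficiency, not as an invalid test. For pooled active v placebo, baseline adjustment gains 16.9, 8.9 and 1.8 percentage points over a change score at ρ = 0.3, 0.5 and 0.7, and 3.3, 8.9 and 15.0 points over week 8 alone. For that contrast, power above 90% is reached with adjustment at ρ = 0.5 but not at ρ = 0.3, so the stated figure needs a stated correlation.

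These sizes assume that 9% is a single-scan SD, that the effect is 8%, and that one two-sided test is done at 0.05. If 9% is already the SD of change, change-score power is 83.4% for 45 v 15 whatever ρ is, and the variance ratio (1+ρ)/2 in favour of adjustment still applies. All figures are for one connection. With 361 × 360 / 2 = 64,980 distinct pairs under FDR control, power per connection would be expected to be lower under any of these models.

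**What to change.** In item 3, replace the group-wise ANOVA with a linear model fitted for each connection: week-8 FC as outcome, randomised arm as the factor of interest, and the same participant's baseline FC as covariate. Apply the FDR step to the p-values of the between-arm term. State the contrast (pooled active v placebo, or each arm v placebo). Then restate power for that model and contrast, saying whether 9% is the SD of a scan or of a change and which within-person correlation is assumed.

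A mixed model testing group-by-time should not be offered as interchangeable. With two visits and a freely estimated baseline mean in each arm, it reproduces the change-score test and has that test's lower power.

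The cost is SAP wording, a different model call and a recalculated power sentence. The baseline scans are already scheduled, so no scans, visits or participants are added.
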